24.1 Study Intervention(s) Administered

24.1.1 Investigational Products

AZD4573 will be administered as an absolute (flat) dose, 2-hour (\pm 15 minutes) IV infusion once weekly, at least 5 days apart, alone and in combination with acalabrutinib 100 mg twice daily continuously.

AZD4573 and acalabrutinib will be supplied by AstraZeneca. CC1

Detailed

information on the drug products and administration guidelines are in the AZD4573 Handling Instructions and acalabrutinib participant leaflet.

Table 28 Investigational Products

Intervention Name	AZD4573	Acalabrutinib
Type	Drug	Drug
Dose Formulation	Concentrate for solution for infusion	Capsules
Unit Dose Strength(s)	1.5 mg/mL	100 mg
Dose	Part A Period 1: 12 mg* Part A Period 2: dose to be established based on emerging data from Module 1	100 mg BID
Route of Administration	IV infusion	Oral
Use	Experimental	Experimental
IMP and NIMP	IMP	IMP

Intervention Name	AZD4573	Acalabrutinib
Sourcing	Provided centrally by AstraZeneca	Provided centrally by AstraZeneca
Packaging and Labelling	Study Intervention will be provided in vials. Each vial will be labelled as required per country requirement	Study Intervention will be provided in bottles. Each bottle will be labelled as required per country requirement
Current/Former Name(s) or Alias(es)	AZD4573/ AZ13810325	Acalabrutinib/ACP-196 /Calquence

*In Period 1, target dose of 12 mg achieved through intra-patient ramp up from starting dose on Day 1 (6 mg), with subsequent titration to the intermediate dose on Day 8 (9 mg), and to target dose of 12 mg on Day 15.

Abbreviations: BID = twice daily; IMP = investigational medicinal product; IV = intravenous;
NIMP = non-investigational medicinal product.

Labels will be prepared in accordance with Good Manufacturing Practice and local regulatory guidelines and will be translated into the local language. The labels will fulfil Good Manufacturing Practice Annex 13 requirements for labelling.

All IPs should be kept in a secure place under appropriate storage conditions. The IP label on the vial (AZD4573) or bottle (acalabrutinib) specifies the appropriate storage conditions.

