In general, if a participant experiences a Grade 1 or Grade 2 haematological or non-haematological toxicity, no dose modification is required. If a participant experiences a Grade 3 or Grade 4 toxicity, not attributable to the disease or disease-related processes under investigation, dosing will be interrupted and/or the dose reduced (see [Table 30](#) for acalabrutinib reduction options and [Table 31](#) for recommended dose modifications for AZD4573 and acalabrutinib) and supportive therapy administered as required. If the toxicity resolves or reverts to CTCAE Grade ≤ 2 within 21 days and the participant was showing clinical benefit, treatment with study treatment(s) may be restarted.

If the toxicity does not resolve to CTCAE Grade ≤ 2 within 21 days, then the participant should be withdrawn from the study and observed until resolution of the toxicity. Maximal drug interruption allowed for related toxicity for both AZD4573 and acalabrutinib is ≤ 21 consecutive days.

Table 31 Recommended Dose Modifications for AZD4573 and Acalabrutinib

Event ^a	Occurrence	Action with AZD4573	Action with Acalabrutinib
Tumour Lysis Syndrome (TLS) – Howard Modification of Cairo-Bishop Criteria			
Changes in uric acid, potassium, phosphorus, creatinine or calcium, or symptoms suggestive of clinically significant TLS, in the Investigator's judgement	Any	For any abnormal changes present before dosing, initiate supportive therapy and hold drug for up to 7 days. If not resolved, reduce by 1 dose level.	Withhold acalabrutinib until resolved, resume dosing at the same dose level upon resolution.
		For events of Grade 1 or 2 TLS, resume at same dose level upon resolution.	For events of Grade 1 or 2 TLS, resume at same dose level upon resolution.
	For 1st occurrence of Grade 3 TLS resume at the same dose upon resolution to Grade 1.	For 1st occurrence of Grade 3 TLS resume at the same dose upon resolution.	
	For 2nd occurrence of Grade 3 TLS, after resolution to Grade 1, reduce dose by one dose level when restarting AZD4573 except events that in the opinion of the Investigator, in consultation with the Medical Monitor, are not dose-limiting.	For 2nd occurrence of Grade 3 TLS, after resolution to Grade 1, reduce dose by one dose level when restarting or discontinue acalabrutinib except events that in the opinion of the Investigator, in consultation with the Medical Monitor, are not dose-limiting.	

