24.9.1 Retreatment Criteria

Retreatment is defined as the first dose of study drug after a significant period of intentional pause in study drug treatment (other than missed doses, eg, study treatment put on hold until resolution of COVID 19)

Retreatment criteria (criteria to be met before participant restarts study drug infusions [and capsules, as applicable]):

All participants:

- 1 Participant has recovered from all treatment-related non-haematological toxicity to CTCAE Grade ≤ 2 .
- 2 Recovery of neutrophils $\geq 1000/\mu\text{L}$ and platelets $\geq 50,000/\mu\text{L}$.
- 3 Participant has recovered from all hepatic toxicity events within the timeframes described in [Table 32](#) above. If biochemical changes in transaminase(s) and total bilirubin are consistent with the definition of Hy's Law, the participant may continue to receive study drug only if all abnormalities have resolved within the timeframes specified in [Table 32](#) above, there are no symptoms of liver injury and INR has not increased above $1.5 \times \text{ULN}$ (or $1.5 \times \text{baseline}$). In these circumstances the participant must be made aware of the unknown potential for liver damage with continued exposure to AZD4573 prior to retreatment. Documentation of continued consent is required.
- 4 Recovery of uric acid to $< \text{ULN}$.
- 5 Recovery of changes in uric acid, potassium, phosphorus, creatinine or calcium, or symptoms suggestive of TLS as defined in [Table 31](#).
- 6 In case of any new deterioration in laboratory values, not fulfilling eligibility criteria and deemed as clinically significant by the Investigator, the Medical Monitor must be contacted to discuss whether AZD4573 dosing can be continued.

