25.2 Patient Withdrawal from the Study

Please refer to Section [7.2](#) for information on participant withdrawal from the study.

In addition for Module 2, participants who experience an AE during the dosing ramp up (Period 1 Weeks 1-3) that result in inability to complete the dosing ramp up will permanently discontinue AZD4573 and exit the study.

25.3 Procedures for Handling Participants Incorrectly Initiated on AZD4573 or Combination Therapy

Please refer to Section [7.3](#) for information on procedures for handling participants incorrectly initiated on AZD4573 or combination therapy.

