26.1.10.3 TLS Prophylaxis, Monitoring, and Management

Please refer to [Appendix F](#) for definitions of the Howard modification of Cairo-Bishop criteria for clinical and laboratory TLS.

All participants will receive TLS prophylaxis during the intra-patient ramp up and be monitored for TLS during the first 24 hours post start of dose. Monitoring for TLS includes checking potassium, calcium, phosphate, uric acid, and creatinine. Fluid balance must be monitored according to institutional standards.

Participants will be required to be monitored for TLS for up to 24 hours post dose until they have received at least one AZD4573 dose at the target dose level (ie, for at least the first 3 AZD4573 once-weekly doses). If a participant has no signs of laboratory TLS at the 6-hour TLS monitoring assessment, the participant may leave the clinic after the collection of other laboratory samples, as per the SoA, at 7 hours after the start of the infusion and managed as an outpatient, at the discretion of the Investigator. These participants must return to the clinic the next morning to complete the 24 hour TLS monitoring period as per the SoA (Cycle 1 Weeks 1-3). Participants with TLS at the 6-hour TLS monitoring assessment must be admitted for in-patient TLS monitoring for a minimum of 24 hours after the start of the infusion and monitored every 4 to 6 hours during this time (or more frequently if clinically indicated).

Sites retain the option to hospitalise participants based on clinical judgement, despite normal TLS laboratory results 6 hours after the start of the infusion. Admitting the participant for subsequent dose administrations will be done at Investigator discretion.

Any hospitalisation due to occurrence of an AE must be reported as an SAE, per definition. However, if hospitalisation is purely for the purposes of extended observation then this does not qualify as an SAE and does not need to be reported.

For all participants, results of safety laboratory testing (haematology and clinical chemistry at a minimum) must be available within 72 hours prior to dosing and must be reviewed by the Investigator prior to each administration of AZD4573.

In particular, the uric acid level must be < ULN prior to the start of each AZD4573 infusion.

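### Table 31 sets no resolution condition for the reduced AZD4573 dose after a predose TLS hold, which for uric acid contradicts the rule that it be below ULN before every infusion

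*Protocol*

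**What the plan says.** The TLS row of Table 31 (protocol Section 24.9) covers changes in uric acid, potassium, phosphorus, creatinine or calcium, and suggestive symptoms. Where such changes are present before dosing, the AZD4573 column calls for supportive therapy and then "hold drug for up to 7 days. If not resolved, reduce by 1 dose level". The acalabrutinib column of the same row reads "Withhold acalabrutinib until resolved, resume dosing at the same dose level upon resolution". The next AZD4573 line reads "For events of Grade 1 or 2 TLS, resume at same dose level upon resolution". The lines for a first and a second Grade 3 event both make the restart wait for resolution to Grade 1.

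Other passages set conditions on giving AZD4573:

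- Section 26.1.10.10.3 (TLS Prophylaxis, Monitoring, and Management): "the uric acid level must be < ULN prior to the start of each AZD4573 infusion". A note in the same section asks for hyperuricaemia at Screening or during the ramp-up to be treated so that uric acid is below ULN before each administration.
- Table 34, footnote d: the same threshold before each dose, worded as a recommendation.
- Section 24.9.1 (Retreatment Criteria): criterion 4 asks for uric acid to be back below ULN. Criterion 5 begins "Recovery of changes in uric acid, potassium, phosphorus, creatinine or calcium", adds suggestive symptoms, and then points to Table 31 for the definition.

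On the ramp-up, the footnote to Table 28 describes a "target dose of 12 mg achieved through intra-patient ramp up from starting dose on Day 1 (6 mg" through 9 mg on Day 8 to 12 mg on Day 15. Section 25.2 says that participants with an AE in Weeks 1 to 3 "that result in inability to complete the dosing ramp up will permanently discontinue AZD4573 and exit the study".

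**The concern.** TLS is listed in Table 25 as an important identified risk of AZD4573, and this row is the dosing instruction for it. If uric acid is still above ULN when the 7-day hold ends, the table points to a lower dose and Section 26.1.10.10.3 points to no infusion. Two sites could act differently on the same laboratory result, each following the protocol, and under one reading drug is given with an unresolved abnormality.

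The analysis is affected too. Table 26 lists dose modifications and treatment discontinuation due to AE among the Part A primary endpoints. What is recorded there would partly reflect which passage a site followed.

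**Working it through.** No figure in the plan needs recomputing. The check sets the passages against one case: a participant with an abnormal predose value that has not resolved after a 7-day hold of AZD4573.

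1. **Table 31, predose line.** The trigger for the reduction is that the value has not resolved, and the hold itself is limited to 7 days. Nothing in the line extends the hold or makes the reduced dose wait. Literal result: dose at one level lower.
2. **Other lines in the row.** The Grade 1 or 2 line and the first and second Grade 3 lines each state a resolution condition. Later Grade 3 events go to discussion with the Medical Monitor, and Grade 4 means discontinuation. The predose line is the only one that leads to a stated AZD4573 dose level without requiring resolution.
3. **If the value is uric acid.** Section 26.1.10.10.3 makes a level below ULN mandatory before each infusion. Table 34 footnote d, the hyperuricaemia note and retreatment criterion 4 point the same way. Result: no infusion. This contradicts step 1.
4. **If the value is potassium, phosphorus, creatinine or calcium.** The uric acid rules do not apply. Criterion 5 asks for recovery but defines it by reference to Table 31, so the reader is sent back to step 1. Section 24.9.1 also applies only after a significant intentional pause and does not say whether a hold of up to 7 days counts. Result: unsettled.
5. **General interruption limit.** Section 24.9 also states: "Maximal drug interruption allowed for related toxicity for both AZD4573 and acalabrutinib is ≤ 21 consecutive days". It does not say whether a predose TLS hold may continue from day 7 towards day 21.
6. **Ramp-up.** Section 22.1 fixes 6 mg in Week 1, 9 mg in Week 2 and 12 mg from Week 3. Assume that a dose level means one of these steps. One level down from 12 mg is then 9 mg, one level down from 9 mg is 6 mg, and the text available names nothing below 6 mg. A reduction therefore departs from the schedule, and no passage says whether it is a permitted delay or an inability to complete the ramp-up under Section 25.2. Table 30 gives reduction levels for acalabrutinib only.

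**The case against.** The strongest reply is that the passages can be read together. Table 31 is headed as recommended modifications and sets the level, while Sections 24.9.1 and 26.1.10.10.3 set the condition for restarting. An abnormality that outlasts 7 days would then mean a restart one level lower once it has recovered. Neighbouring lines follow that pattern, and the reading is possible. It is not written, however, and the line states a 7-day limit on the hold where that reading would need the hold to continue. A dosing instruction that needs this reconstruction is at best ambiguous.

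Three further objections stand and limit the point:

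- The explicit below-ULN rule covers uric acid only.
- Acalabrutinib is given only in Period 2, where Section 22.1 requires no further ramp-up. Its cell shows the contrast within the row but has no bearing on the ramp-up question.
- Only the second part of the protocol was available. AZD4573 dose levels may be defined in the core dose modification section (6.12), so their absence cannot be asserted.

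Section 18.5 also refers to a decision to permanently halt enrolment. That may leave few or no new ramp-ups, but the predose conflict remains for anyone still being infused, and Section 23.6 allows treatment to continue after the primary analysis.

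**Conclusion.** The contradiction holds for uric acid. For the other four analytes, the protocol gives no clear answer because its one recovery rule refers back to the row in question. The relation of a dose reduction to the ramp-up and to Section 25.2 is a secondary gap, subject to what the core section says.

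A reader might infer three stronger points that the documents do not support:

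- **That the row cannot be used during the ramp-up.** The hold, supportive therapy, resumption on resolution and Grade 4 discontinuation can all be applied in Weeks 1 to 3. Section 25.2 applies only where an AE makes the ramp-up impossible to complete, and a repeated or delayed step does not by itself do that.
- **That the rule would be used mainly in those weeks, because Table 23 places TLS monitoring there.** Section 26.1.7 puts all five analytes in the predose chemistry panel, which continues through later cycles in both periods.
- **That a primary endpoint rate would shift by a given amount.** One participant in 12 is 1/12 = 8.3 percentage points, but that is true of any single participant. The documents give no count of those affected, and Section 27.1 plans no hypothesis test.

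The importance of the point lies in the conflicting instruction for an important identified risk, not in a calculated effect.

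**What to change.** Reconcile the predose AZD4573 line of the Table 31 TLS row with Section 24.9.1 (criteria 4 and 5), Section 26.1.10.10.3 and Table 34 footnote d. One statement should say, for each of the five analytes, whether AZD4573 may be infused while an abnormality is unresolved. Criterion 5 should no longer depend on Table 31 for its meaning. State also whether Table 31 or Section 25.2 governs a one-level reduction during the ramp-up, with a pointer to wherever AZD4573 dose levels are defined. The sponsor and the Safety Review Committee choose the rule; this review does not propose one.

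The cost is wording in one table row and a few cross-references, with no new procedures or participants.

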Grade 2 Isolated ALT/AST > 3 to $\leq 5 \times$ ULN or Isolated Bilirubin > 1.5 to $\leq 3 \times$ ULN	After 7 days if hepatic enzymes resolve to Grade ≤ 1 , rechallenge at same dose level.	Withhold or continue acalabrutinib (at Investigator discretion, after discussion with the Medical Monitor). To prevent disease progression, monitor disease parameters closely. Monitor ALT, AST, ALP, and bilirubin at least 1x per week. After 7 days if hepatic enzymes appear to be improving and acalabrutinib was withheld, restart acalabrutinib at current dose level.

Event ^a	Action	
	AZD4573	Acalabrutinib
Grade 3 Isolated ALT/AST > 5-20 × ULN	If recovered to Grade ≤ 1 within 7 days, allow rechallenge at same dose level. If not recovered to baseline level within 7 days, discontinue AZD4573.	Withhold or continue acalabrutinib (at Investigator discretion, after discussion with the Medical Monitor). To prevent disease progression, monitor disease parameters closely.
Grade 3 Isolated Bilirubin > 3-10 × ULN	If recovered to baseline level within 96 hours (-2/+12 hours) of the start of the infusion allow rechallenge at same dose level. If not, discontinue AZD4573	Monitor ALT, AST, ALP, and bilirubin at least 1x per week. After 7 days if hepatic enzymes appear to be improving and acalabrutinib was withheld, restart acalabrutinib with 1 level dose reduction or discontinue.
Grade 4^c Isolated ALT > 20 × ULN or Isolated Bilirubin > 10 × ULN	Discontinue AZD4573.	Discontinue acalabrutinib.
Grade 4 Isolated elevation ($\geq 20 \times$ ULN) in AST without concomitant elevation in ALT $\geq 20 \times$ ULN or concomitant elevation in TBL $\geq 2 \times$ ULN that fails to return to baseline level within 7 days from start of dosing	Discontinue AZD4573.	Discontinue acalabrutinib.
Grade 4^c Isolated AST elevation $\geq 20 \times$ ULN without concomitant elevation in ALT $\geq 20 \times$ ULN or TBL $\geq 2 \times$ ULN	1st occurrence If recovered to Grade ≤ 1 or baseline level within 7 days of the start of the infusion allow rechallenge at same dose level	Withhold or continue acalabrutinib (at Investigator discretion, after discussion with the Medical Monitor). To prevent disease progression, monitor disease parameters closely.
	2nd occurrence If recovered to Grade ≤ 1 or baseline level within 7 days of the start of the infusion allow rechallenge with 1 dose level reduction	Monitor ALT, AST, ALP, and bilirubin at least 1x per week. After 7 days if hepatic enzymes appear to be improving and

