Event ^a	Action	
	AZD4573	Acalabrutinib
	3rd occurrence Discontinue AZD4573	acalabrutinib was withheld, restart acalabrutinib at current dose level at the 1st occurrence and with 1 level dose reduction at the 2nd occurrence . Discontinue acalabrutinib at the 3rd occurrence .
Concurrent elevations in ALT, AST, or bilirubin (Please also refer to Appendix E for actions to be taken in the event of PHL)		
ALT or AST $\geq 3 \times$ ULN with TBL $\geq 2 \times$ ULN (PHL) AND INR $\geq 1.5 \times$ ULN (or $\geq 1.5 \times$ baseline if elevated at baseline) of any duration	Discontinue AZD4573.	Discontinue acalabrutinib.
ALT or AST $\geq 3 \times$ ULN with the appearance of fatigue, nausea, vomiting, right upper quadrant pain or tenderness, fever, rash, and/or eosinophilia $> 5\%$	Discontinue AZD4573.	Discontinue acalabrutinib.
ALT or AST $\geq 3 \times$ ULN and TBL $\geq 2 \times$ ULN where TBL does not return to baseline level within 96 hours (-2/+12 hours) from start of dose and/or AST or ALT do not return to baseline level within 7 days from start of dose	Discontinue AZD4573.	Discontinue acalabrutinib.
Grade 3 elevation ($\geq 5 \times$ ULN) in ALT or AST with TBL elevation above baseline level or ULN, but $< 2 \times$ ULN that do not return to baseline level within 7 days	Discontinue AZD4573.	Discontinue acalabrutinib.
ALT and AST $\geq 3 \times$ ULN with concomitant TBL $\geq 2 \times$ ULN, NO increase in INR $\geq 1.5 \times$ ULN (or $1.5 \times$ baseline), and NO fatigue, nausea, vomiting, right upper quadrant pain or tenderness, fever, rash, and/or eosinophilia $> 5\%$	If recovered to Grade ≤ 1 or baseline level within 96 (-2/+12) hours, rechallenge at same dose level ^c	Withhold acalabrutinib until recovered. Once recovered, restart acalabrutinib at same dose.

^a Adverse reactions are graded using National Cancer Institute CTCAE version 5.0. All grades refer to CTCAE grading except for TLS, which uses the Howard modification of Cairo-Bishop criteria ([Howard et al 2011](#)).

- ^b Elevations in ALT or AST are considered isolated if bilirubin remains below Grade 1, and elevations in bilirubin are considered isolated if ALT and AST remain below Grade 1.

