26.1.10.9 Liver Chemistry Test Abnormalities and the Risk of Liver Injury

Transaminase elevations are an important potential risk for patients treated with acalabrutinib, and an important identified risk for participants treated with AZD4573. Reactivation of hepatitis B infection has been observed in patients treated with acalabrutinib. Participants should be made aware of the risk of possible overlapping toxicities of transaminase elevations while receiving both drugs. Evidence of abnormal liver chemistry should be monitored as per the protocol guidelines. Increased levels of AST, ALT, or serum bilirubin should trigger an investigation of the cause, which may include viral infection or disease progression with liver infiltration. The Investigator should consider whether the abnormal liver chemistry meets the criteria for expedited reporting.

Bilirubin increase with transaminase increase is included as an important identified risk for AZD4573. Biochemical changes of increased transaminases with concomitant increase in

bilirubin fulfilling criteria for Hy's law have been observed in participants treated with AZD4573. These events resolve rapidly and have to date not been associated with any adverse clinical sequelae or lasting liver damage. Upon rechallenge with AZD4573, there is no consistent pattern of recurrence, nor is there any consistent increase in severity of the events. As such, while the events follow the biochemical definition of Hy's law, the clinical pattern is rapidly self-limiting and does not seem to predict any lasting liver damage.

Participants who experience elevated ALT/AST $\geq 3 \times$ ULN and/or elevated total bilirubin $\geq 2 \times$ ULN after AZD4573 dosing must be closely monitored with repeated liver chemistry tests (INR, fibrinogen, D-dimer [where available at institution], ALP, ALT, AST, GLDH if a GLDH test cannot be performed at the site or locally, LDH will be sufficient), CPK, total bilirubin, direct bilirubin, indirect bilirubin) are required at least every 48 hours (-2/+12 hours) after the start of the infusion and until resolution of the event. **CCI** will also be collected (see Section [26.8](#))

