If bilirubin fails to resolve within 96 hours (-2/+12 hours) or transaminases fail to resolve within 7 days, or if the event is associated with significant clotting abnormality or clinical symptoms of liver disease, study treatment must be permanently discontinued (the participant remains on study for the 30-day SFU and long-term follow-up [LTFU] visits), and the event must be immediately communicated to AstraZeneca.

For guidance on treating liver toxicity, please refer to [Table 32](#) of this protocol.

During the course of the study the Investigator will remain vigilant for increases in liver biochemistry. The Investigator is responsible for determining whether a participant meets PHL criteria at any point during the study.

Please refer to [Appendix E](#) for the process to be followed to identify and appropriately report events of PHL. It is not intended to be a comprehensive guide to the management of elevated liver biochemistries.

The Investigator will participate, together with the Medical Monitor, in review and assessment of PHL events to agree whether HL criteria are met. HL criteria are met if there is no alternative explanation for the elevations in liver biochemistry.

The Investigator is responsible for recording data pertaining to PHL/HL cases and for reporting AEs and SAEs according to the outcome of the review and assessment in line with standard safety reporting processes.

Regarding the hepatic toxicity events encountered to date with AZD4573, it has been observed that while the biochemical changes of increased transaminase with concomitant elevation in

bilirubin seen in some participants could be classified as HL by its strict definition, they do not follow a pattern that is consistent with true HL predictive of hepatic injury, and are therefore 'PHL' cases. The events are rapidly resolved and to date have not led to any clinical sequelae or lasting hepatic injury. Repeated dosing with AZD4573 following these events has demonstrated that there is no consistent pattern of recurrence and no consistent increase in severity of the events if they do recur.

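### In Module 2, Table 32 lets AZD4573 be re-dosed after 7 days for isolated bilirubin of 2 to 3 × ULN, while section 26.1.10.9 requires a permanent stop if that bilirubin is unresolved at 96 hours

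*Protocol*

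**What the plan says.** **Table 32, Grade 2 row (section 24.9).** One row covers isolated ALT/AST above 3 and up to 5 × ULN, or isolated bilirubin above 1.5 and up to 3 × ULN. Its only AZD4573 instruction is "After 7 days if hepatic enzymes resolve to Grade" 1 or lower, rechallenge at the same dose level. The acalabrutinib cell lets the investigator withhold or continue after discussion with the Medical Monitor, then says "After 7 days if hepatic enzymes appear to be improving and acalabrutinib was withheld, restart acalabrutinib at current dose level".

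**Table 32, footnote b.** "elevations in bilirubin are considered isolated if ALT and AST remain below Grade 1".

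**Table 32, Grade 3 isolated bilirubin.** For AZD4573: "If recovered to baseline level within 96 hours (-2/+12 hours) of the start of the infusion allow rechallenge at same dose level". Otherwise AZD4573 is stopped. The acalabrutinib cell is shared with isolated Grade 3 ALT/AST and ends "After 7 days if hepatic enzymes appear to be improving and acalabrutinib was withheld, restart acalabrutinib with 1 level dose reduction or discontinue".

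**Section 26.1.10.9.** The section applies to ALT/AST of at least 3 × ULN and/or total bilirubin of at least 2 × "ULN after AZD4573 dosing must be closely monitored with repeated liver chemistry tests". One ground for stopping is timing: "If bilirubin fails to resolve within 96 hours (-2/+12 hours) or transaminases fail to resolve within 7 days". The others are a marked coagulation disturbance and symptoms pointing to the liver. On any of these grounds, "study treatment must be permanently discontinued (the participant remains on study for the 30-day SFU" visit and for later follow-up contact. It then refers the site to Table 32 for guidance on treating liver toxicity.

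**The concern.** Elsewhere the module keeps two separate clocks: 96 hours for bilirubin and 7 days for transaminases. Section 26.1.10.9 does so, and so do the split Grade 3 AZD4573 cells and the discontinuation row in Table 32 for raised transaminases with bilirubin of 2 × ULN or more. The Grade 2 row is the exception, since it puts both analytes on the transaminase clock.

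AZD4573 is infused once weekly, so day 7 is normally the next infusion day. A site following Table 32 could give a full dose to a participant who, under section 26.1.10.9, should already have stopped for good. Another site could stop the same participant. Bilirubin increase with transaminase increase is an important identified risk of this drug. Dose modifications and discontinuations due to adverse events are also primary endpoints of Module 2 (Table 26), so what is recorded would depend on which page the site followed.

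**Working it through.** This is a comparison of rules; the plan gives no figure to reproduce.

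**Step 1: where the rules overlap.**
- Table 32, Grade 2 isolated bilirubin: above 1.5 and up to 3 × ULN.
- Section 26.1.10.9 trigger: 2 × ULN or more. It is worded and/or, so bilirubin alone is enough.
- Intersection: 2 to 3 × ULN. Above 1.5 but below 2 × ULN, section 26.1.10.9 is not triggered and there is no conflict.

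**Step 2: what each rule asks in the overlap.**

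| | Table 32, Grade 2, AZD4573 | Section 26.1.10.9 |
|---|---|---|
| Test | hepatic enzymes at Grade 1 or lower | bilirubin resolved |
| Time | 7 days | 96 h (-2/+12 h) |
| If met | rechallenge, same dose | no stop on bilirubin grounds |
| If not met | nothing stated | permanent discontinuation |

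**Step 3: the time gap.** The 96-hour window runs from 96 - 2 = 94 h to 96 + 12 = 108 h. Seven days is 7 × 24 = 168 h. Rechallenge therefore falls 168 - 108 = 60 h to 168 - 94 = 74 h after the stop was due (72 h from the nominal time). This assumes that the 7 days run from the start of the infusion, which the Grade 2 cell does not say. If they run from the onset of the abnormality, the gap is longer.

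**Step 4: does the reading of *hepatic enzymes* matter?** Read literally, footnote b means that ALT and AST are already below Grade 1 in an isolated bilirubin event. The condition is then met from the outset and bilirubin is not tested. Read loosely, to include bilirubin, the conflict remains. Take bilirubin of 2.2 × ULN at 96 h and 1.4 × ULN on day 7, with normal transaminases and a normal baseline.
- Table 32: 1.4 is at or below 1.5 × ULN, so Grade 1 or lower, and the participant is rechallenged at the same dose.
- Section 26.1.10.9: 2.2 × ULN at 96 h is still above the section's own trigger of 2 × ULN, so it is unresolved and the participant stops permanently. The section does not define *resolve*, but this value fails on baseline, on Grade 1 and on the trigger itself.

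**Step 5: does other visible text decide between them?**
- Section 24.2 has a 96-hour bilirubin stop, but only for Potential Hy's Law, which needs raised transaminases as well.
- Section 24.9.1, criterion 1, accepts recovery to Grade 2 or lower, which for bilirubin extends to 3 × ULN. Criterion 3 requires recovery from hepatic events but takes its timeframes from Table 32.
- Section 26.1.7 requires liver tests at 48 and 96 h for bilirubin of 2 × ULN or more, and says to contact the medical monitor if the event is unresolved at 96 h. It does not say what to do with the dose.
- The general text of section 24.9 says that Grade 1 or 2 toxicity usually needs no dose modification, which points towards re-dosing.

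None of these states a precedence.

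**The case against.** The best case for leaving the text alone is that the two places differ in force. Table 32 is headed as recommended dose modifications and is cited as guidance, whereas section 26.1.10.9 uses mandatory language and requires immediate communication to the sponsor. A careful site would let the mandatory rule win. Section 26.1.7 also brings in the medical monitor at 96 h, before the next weekly infusion. Both points stand as reasons why a wrong infusion is less likely. They do not remove the conflict, because no precedence is written and section 26.1.10.9 itself sends the site to the table that contradicts it.

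It is also fair to say that *hepatic enzymes*, in a cell shared by ALT/AST and bilirubin, is probably loose shorthand for whichever value was raised, and that criterion 3 of section 24.9.1 would block a restart after an intentional pause if bilirubin were still high on day 7. A reader might infer from the literal wording that the protocol intends re-dosing with bilirubin never checked. The documents do not establish that intent. The point rests on timing, which survives the generous reading.

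A reader might also infer that the acalabrutinib cells for Grades 2 and 3 contradict section 26.1.10.9 in the same way. That depends on *study treatment* there meaning both drugs. The reference to the 30-day visit, which is timed from the last dose of all study drug, favours that meaning. However, the trigger is elevation after AZD4573 dosing, section 24.10 allows acalabrutinib to continue alone after AZD4573 stops, and the Grade 3 cell itself offers discontinuation. This is an ambiguity to resolve, not an established contradiction.

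Finally, only the second part of the protocol is shown. The core sections on dose modification (6.12) and discontinuation (7.1) are not visible and could bear on precedence.

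**Conclusion.** The contradiction holds for AZD4573 in Module 2, for isolated bilirubin of 2 to 3 × ULN that has not resolved by 96 h (-2/+12 h). Table 32 permits a same-dose rechallenge on day 7; section 26.1.10.9 requires a permanent stop some 60 to 74 h earlier, if the 7 days are counted from the start of infusion. There is no conflict for events that resolve by 96 h, nor below 2 × ULN. The AZD4573 cell for Grade 3 isolated bilirubin agrees with section 26.1.10.9.

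The conclusion rests on reading the 26.1.10.9 stop as covering every event its and/or trigger admits, and on the visible text only. A reader might infer that many participants are exposed, or that the primary safety endpoints would move by a material amount. The documents do not support a figure for either. They do not give the frequency of such events or the number still on treatment in a module planned for about 12 participants, and section 18.5 reports that enrolment has been permanently halted. The number affected is therefore unknown and probably small. The change is worth making because it concerns the safety of those still being dosed and costs almost nothing.

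**What to change.** 1. In Table 32, split isolated bilirubin out of the Grade 2 AZD4573 cell. For isolated total bilirubin of 2 × ULN or more, apply the 96-hour (-2/+12 h) bilirubin criterion of section 26.1.10.9 and the Grade 3 bilirubin cell; if it is not met, discontinue AZD4573.
2. Wherever the event is isolated bilirubin, make the recovery test refer to bilirubin, not hepatic enzymes.
3. State in section 26.1.10.9 whether the stop on study treatment includes acalabrutinib, and align the Grade 2 and Grade 3 acalabrutinib cells with the answer.

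The cost is rewording one AZD4573 cell, one clarifying sentence in section 26.1.10.9, and matching edits to two acalabrutinib cells. The 96-hour bilirubin result is already collected under section 26.1.7, so there is no new test or visit. For AZD4573 at 2 × ULN or more, the change stops nobody whom section 26.1.10.9 does not already require to stop.
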